**One、 Research purpose and main research content**

**Purpose of the study:**

To evaluate and compare the efficacy and safety of recombinant human adenovirus type 5 injection combined with TACE-based comprehensive therapy in patients with primary hepatocellular carcinoma with portal vein tumor thrombus in stage IIIa.

**The main research contents:**

This study is the first to compare the efficacy and safety of recombinant human adenovirus type 5 injection via hepatic artery infusion combined with TACE-based combination therapy for the treatment of patients with primary hepatocellular carcinoma with portal vein carcinoma thrombosis in stage IIIa, providing a safe and reliable treatment for the clinical management of this group of patients, as well as a reference and basis for the treatment of other tumors with this new treatment modality.

**Two、 Research background and basis (research status at home and abroad, development trend, necessity, novelty, innovation, research significance)**

According to statistics, hepatocellular carcinoma (hereafter referred to as hepatocellular carcinoma) accounts for 80% of primary liver cancer worldwide, has a heavy disease burden, and is the leading cause of cancer-related deaths in many parts of the world. Hepatocellular carcinoma is insidious in origin and develops rapidly, and most patients have local progression or distant metastasis by the time they are diagnosed, especially the formation of portal vein thrombosis. The incidence of hepatocellular carcinoma with portal vein thrombosis is high and the disease progresses rapidly, and the available treatments are limited and ineffective.

It has been found that through palliative treatments such as transarterial chemoembolization (TACE) and neoadjuvant three-dimensional conformal radiotherapy, some patients can experience regression or even disappearance of portal vein cancer thrombus, tumor volume reduction, and disappearance of satellite foci, thus reducing the stage of the lesion, increasing the surgical resection rate, and prolonging patient survival. TACE is the treatment of choice for unresectable or intermediate to advanced hepatocellular carcinoma, which is widely used in clinical practice with positive effects, but the tumor is prone to recurrence and metastasis after TACE. Therefore, in most cases, TACE is combined with other therapies to treat hepatocellular carcinoma.

Recombinant human adenovirus type 5 injection (H101) is a structural modification of wild-type human type 5 adenovirus, with the deletion of E1B 55KD fragment and E3 partial fragment, based on the characteristic that P53 pathway disorder is common to tumors. The deletion of E3 fragment enhanced the TNF-induced tumor lysis effect, enhanced the immune system's recognition and killing of the virus and infected tumor cells, induced immune infiltration, and activated specific anti-tumor immunity, so that the recombinant human adenovirus type 5 could play the role of precise tumor lysis and systemic immunity.

This study is the first to compare the efficacy and safety of recombinant human

adenovirus type 5 injection via hepatic artery infusion combined with TACE-based combination therapy for the treatment of patients with stage IIIa primary hepatocellular carcinoma with portal vein carcinoma thrombosis, providing a safe and reliable treatment method for the clinical treatment of this group of patients, and also providing a reference and basis for the treatment of other tumors with this new treatment model.

### **Three、 Research methods and technical routes**

#### **Research methods:**

##### 1. Experimental Design

This is a prospective, single-arm study to evaluate the efficacy and safety of recombinant human adenovirus type 5 injection combined with TACE-based combination therapy in patients with primary hepatocellular carcinoma with portal vein carcinoma thrombosis in stage IIIa. Subjects will be screened and evaluated at the study center, and after determining that they meet the inclusion criteria, enrolled patients will be treated with recombinant human adenovirus type 5 injection via hepatic artery infusion combined with TACE regimen. The study is divided into screening period, baseline period, treatment period, and follow-up period. Follow-up after the end of treatment will be every 3 months until death or the end of this study.

##### 2. Method of administration

1) Recombinant human adenovirus type 5 injection: Recombinant human adenovirus type 5 injection is administered intratumorally 48-72h prior to TACE treatment. Before administration, the recombinant human adenovirus type 5 injection was diluted to 30% of the total tumor volume with normal saline. H101 dose:

① The sum of the maximum diameters of the lesions was  $\leq 10\text{cm}$ , and the total dose was  $1.0 \times 10^{12}\text{vp}$  (2 injections);

② The sum of the maximum diameters of the lesions was  $> 10\text{cm}$ , and the total dose was  $1.5 \times 10^{12}\text{vp}$  (3 injections);

2) TACE: According to Seldinger technique percutaneous femoral artery puncture, arteriogram to determine the tumor location, number, size, distribution range and blood supply, microcatheter selectively inserted into the tumor blood supply artery, then slowly injected iodinated oil + chemical drugs fully mixed with emulsion. The specific chemotherapeutic drugs were: oxaliplatin  $85\text{mg}/\text{m}^2$ , calcium folinic acid  $400\text{mg}/\text{m}^2$ , 5-fluorouracil  $1200\text{mg}/\text{m}^2$ , and then super liquid iodinated oil embolization was given according to the intraoperative imaging tumor blood supply.

Recombinant human adenovirus type 5 was administered in combination with TACE in cycles of every 3 weeks for a total of 2-4 cycles. If patients experience serious adverse reactions during this period they need to discontinue the drug.

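### The protocol gives two incompatible routes for H101: hepatic artery infusion in the aim and design text, intratumoral administration in the dosing section

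*Protocol*

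**What the plan says.** Section One, The main research contents, describes the treatment under study as "recombinant human adenovirus type 5 injection via hepatic artery infusion combined with TACE-based combination therapy". The last paragraph of section Two repeats that aim almost word for word: "via hepatic artery infusion combined with TACE-based combination therapy for the treatment of patients with stage IIIa primary hepatocellular carcinoma".

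Section Three, 1. Experimental Design, turns the aim into a statement about the patients: "enrolled patients will be treated with recombinant human adenovirus type 5 injection via hepatic artery infusion combined with TACE regimen".

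Section Three, 2. Method of administration, item 1, then says: "Recombinant human adenovirus type 5 injection is administered intratumorally 48-72h prior to TACE treatment". The same item says that the product is "diluted to 30% of the total tumor volume with normal saline" and sets two dose levels by the sum of the lesion diameters. Arterial access appears only in item 2, for TACE: "According to Seldinger technique percutaneous femoral artery puncture". The closing paragraph fixes the schedule: "Recombinant human adenovirus type 5 was administered in combination with TACE in cycles of every 3 weeks for a total of 2-4 cycles".

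The Purpose of the study speaks only of "efficacy and safety of recombinant human adenovirus type 5 injection combined with TACE-based comprehensive therapy" and names no route. Section Four names none either.

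**The concern.** Placing a drug directly in the tumour and infusing it into the hepatic artery are different procedures with different procedural risks. The design section and the dosing section both tell the site what to do with the same drug in the same patients, and a site cannot comply with both.

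Route is part of what defines the intervention. This is a single-arm study, so whatever response rate or adverse event profile it reports describes the route that was actually used and no other. If patients are treated as item 1 of the administration section says, and the results are then written up under the aim sentence, the conclusions will be credited to a procedure that nobody received. If sites read the protocol differently, the single arm will mix two procedures.

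**Working it through.** The protocol states no figure that bears on this point, so the check compares every statement about how H101 is given.

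| Place in the protocol | Route of H101 | Interval to TACE | Dose and dilution |
|---|---|---|---|
| One, Purpose of the study | none named | none | none |
| One, The main research contents | hepatic artery infusion | none | none |
| Two, last paragraph | hepatic artery infusion | none | none |
| Three, 1. Experimental Design | hepatic artery infusion | none | none |
| Three, 2. Method of administration, item 1 | intratumoral | 48-72 h before | both given |
| Four, Expected goals | none named | none | none |

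**Count.** Three places say arterial and one says intratumoral. Sections One and Two carry nearly the same sentence, so there are about two independent arterial statements against one intratumoral statement. The comparison that matters is Experimental Design against Method of administration, because both are operative text.

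**Could the arterial phrase describe TACE alone?** No. In all three places the infusion phrase follows the drug name directly, and TACE is then added as the thing combined with it. The route belongs to H101.

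**Could both routes be planned?** Nothing says that both are used, that one may replace the other, or that intratumoral is meant to include delivery through the feeding artery.

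**Do the details of item 1 settle it?** They do not.
- The dilution rule, 30% of total tumour volume, fits intratumoral delivery but does not exclude arterial delivery.
- The injection counts work out at 1.0 × 10^12 / 2 = 5 × 10^11 vp and 1.5 × 10^12 / 3 = 5 × 10^11 vp each. The equal amount could mean two or three units of product or two or three needle injections, so it does not identify the route.
- Femoral puncture and catheterisation are described only under TACE. That agrees with intratumoral H101, but it is silence and not a statement.

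**Extent.** The schedule is 2-4 cycles with H101 in each. Assuming one H101 administration per cycle, that is 2-4 administrations per patient. Each one departs from either Experimental Design or Method of administration, so all of them are affected.

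**The case against.** The strongest defence is translation. The English is evidently translated (the technical-route figure keeps a Chinese caption), and item 1 mentions neither a needle nor a percutaneous approach. Intratumoral might therefore be a loose rendering of delivery into the tumour through its feeding artery. The technical-route figure, which is not shown here, may also name the route. Both points limit what can be said about intent. Neither removes the conflict: the ordinary meaning of the word is direct injection, no text supports the looser sense, and whatever the figure shows, the two sections would still disagree in words. If the fault is one of translation, the protocol still carries a wrong route and needs correcting.

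A second defence is that the administration section governs because it is the specific one. The protocol states no order of precedence, so this cannot be assumed. For the same reason a reader should not infer that operators will follow that section. The consequence is conditional on their doing so.

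A reader might also infer that the arterial route would mean a second catheterisation before each TACE, doubling arterial accesses from 2-4 to 4-8 per patient, or a catheter left in place for 48-72 h. The protocol supports neither. The 48-72 h interval is attached only to intratumoral administration, and the arterial statements give no interval, so infusion in the same session as TACE is equally open. It would add no arterial access beyond the 2-4 for TACE.

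**Conclusion.** The contradiction is real and should be corrected before the protocol is relied on. The aim and design text says hepatic artery infusion, the dosing section says intratumoral, and nothing visible reconciles them. It affects every H101 administration over 2-4 cycles. That extent rests on the stated schedule; only the count of 2-4 per patient assumes one administration per cycle.

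The finding goes no further than that. The documents do not show which route was intended: the arterial one is stated more often and in the design section, the intratumoral one stands with the dose and dilution. They do not show that any patient received the wrong route, and they allow no estimate of extra arterial accesses or catheter time.

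**What to change.** Confirm the intended route against the source-language protocol and the technical-route figure, and state that one route wherever H101 administration is described.

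- **If intratumoral:** correct The main research contents in section One, the last paragraph of section Two, and Experimental Design in section Three. Item 1 of Method of administration keeps its route, interval and dilution.
- **If hepatic artery infusion:** correct item 1 of Method of administration. Confirm whether the 48-72 h interval and the dilution to 30% of total tumour volume still apply to arterial delivery, and describe the arterial procedure as it is actually meant to be done, without presuming a catheterisation separate from TACE.

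In either case, report efficacy and safety under the route actually given.

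The cost is small. The intratumoral option is mainly rewording in three places. The arterial option changes one item but needs clinical confirmation of the interval and dilution, so it is more than an edit of one word. Neither requires a change to the single-arm design or to the number of cycles.

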### Technical route:

[figure not shown]

图 1 技术路线图

### The admittance criteria of the research object

#### 1. Inclusion Criteria:

The following criteria must all be met to be included:

- 1) Age  $\geq 18$  years and  $\leq 75$  years, regardless of gender;
- 2) Patients with stage IIIa primary liver cancer diagnosed by histology or imaging;
- 3) ECOG physical status score of 0-1;

- 4) Expected survival time  $\geq 3$  months;
- 5) Received no liver protective and supportive treatment within two weeks before enrollment, and met the following conditions:
  - White blood cell count  $\geq 3.0 \times 10^9/L$ , neutrophil absolute value  $\geq 3.0 \times 10^9/L$ , platelet count  $\geq 50 \times 10^9/L$ , hemoglobin  $> 100g/L$ ;
  - $INR \leq 1.5$  and  $APTT \leq 1.5$  upper limit of normal or partial prothrombin time (PTT)  $\leq 1.5$  upper limit of normal;
  - Total bilirubin (TBIL)  $\leq 2.5$  times the upper limit of normal value; ALT and  $AST \leq 5$  times the upper limit of normal value; Serum creatinine  $\leq 1.5$  times the upper limit of normal value;
  - Creatinine clearance  $\geq 50ml/min$ .
- 6) Voluntary participation in this study and signing of the informed consent form;
- 7) Female patients of childbearing age or male patients whose sexual partners are women of childbearing age are required to use effective contraception throughout the treatment period and for 6 months after the last dose.

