## **2. Exclusion Criteria:**

Any of the following circumstances shall be excluded and shall not be selected:

- 1) Pregnant or lactating women, men or women who do not wish to use effective contraception;
- 2) Patients who have received previous treatment with lysoviruses (e.g., T-VEC), interventional therapy, or TACE;
- 3) Those who are being treated with antiviral drugs;
- 4) having received any other experimental drug, antimicrobial drug, or participated in another interventional clinical trial within 4 weeks prior to enrollment
- 5) Those with a known allergy to the study drug or its active ingredient, or a history of allergy to similar biological agents
- 6) Evidence of Child-Pugh C hepatic function or hepatocellular dysregulation, including those with refractory ascites, ruptured esophageal or gastric variceal bleeding, and hepatic encephalopathy

- 7) presence of a history of immunodeficiency or autoimmune disease or long-term systemic steroid therapy or any form of immunosuppressive therapy within 7 days prior to enrollment
- 8) With any unstable systemic disease, including but not limited to: severe infection, hypertensive patients, uncontrolled diabetes mellitus, unstable angina pectoris, cerebrovascular accident or transient cerebral ischemia, abnormal mental status or active cerebral hemorrhage, myocardial infarction, congestive heart failure, severe arrhythmias requiring drug therapy, renal or metabolic disease, severe hepatic dysfunction (including severe jaundice, hepatic encephalopathy, refractory ascites or hepatorenal syndrome), multiple organ failure with renal dysfunction;
- 9) Previous or concurrent other malignancies;
- 10) Combined medical contraindications that preclude any contrast-enhanced imaging (CT or MRI);
- 11) Other conditions that, in the judgment of the investigator, make the patient unsuitable for participation in this study.

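### Does the identical floor of 3.0 × 10^9/L for white cells and for neutrophils in inclusion criterion 5 call for a change to the entry rules?

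*Protocol*

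**What the plan says.** The protocol's list of inclusion criteria opens with "The following criteria must all be met to be included", so its items combine by a logical AND. The first bullet of item 5 gives the white-cell limit and, directly after it, the neutrophil limit: "White blood cell count $\geq 3.0 \times 10^9/L$ , neutrophil absolute value $\geq 3.0 \times 10^9/L". Both use the same unit and the same value. No other section shown gives a threshold for either count or explains why the two are equal. Under Experimental Design the trial is described as "a prospective, single-arm study".

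**The concern.** A numerical limit is normally written because it decides some cases. Here the white-cell limit decides none, since the neutrophil limit beside it is always at least as strict. Two adjacent, identical figures, one of them inoperative, are what a copying error tends to look like. The figure caption under Technical route is in Chinese, so the English may be a translation and a slip could have arisen there.

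With no comparator arm, the entry rules define the population that the result describes. If a figure in the operative text were wrong, the trial could be turning away patients it meant to enrol, or admitting patients it did not.

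**Working it through.** **Inputs.** From item 5: white cells W ≥ 3.0 and absolute neutrophils N ≥ 3.0, both in 10^9/L. From the opening line of the list: both must hold. From the definition of the counts: N = f × W with 0 ≤ f ≤ 1, taking both from the same blood sample. The protocol states no derived figure on this point, so there is none to reproduce.

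**Redundancy.** Since f ≤ 1, N ≤ W. Hence N ≥ 3.0 gives W ≥ N ≥ 3.0, and no patient can have W < 3.0 and N ≥ 3.0. For example, W = 2.5 fails the white-cell line, but N is then at most 2.5 and fails the neutrophil line too. This follows from the definition and needs no assumption about the patients.

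**Neutrophil share needed to enter, 3.0/W:**

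| W (10^9/L) | 3.0/W | Share needed |
|---|---|---|
| 3.0 | 3.0/3.0 | 100% |
| 3.2 | 3.0/3.2 | 94% |
| 4.0 | 3.0/4.0 | 75% |
| 5.0 | 3.0/5.0 | 60% |
| 6.0 | 3.0/6.0 | 50% |

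**Effective white-cell minimum, 3.0/f.** The protocol gives no neutrophil fractions, so these are assumed: f = 0.4 gives 7.5, 0.5 gives 6.0, 0.6 gives 5.0, 0.7 gives 4.29 and 0.8 gives 3.75. The effective minimum equals the written 3.0 only at f = 1.0.

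**How unusual the line is.** Item 5 sets 4 limits (white cells, neutrophils, platelets, haemoglobin) + 2 (INR, and APTT or PTT counted as one) + 4 (bilirubin, ALT, AST, creatinine) + 1 (creatinine clearance) = 11. Only the white-cell limit is implied by another through arithmetic.

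**What an error, if there were one, would do:**

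- Slip in the English text only: the trial is unaffected.
- White-cell figure meant to be lower: nobody's eligibility changes, because the neutrophil floor still decides.
- White-cell figure meant to be higher, or neutrophil figure meant to be higher: the intended rule is stricter, and some patients admitted under the current text might not have been meant to enter.
- Neutrophil figure meant to be lower: the intended rule is looser, and everyone admitted under the current text still qualifies.
- White cells meant to be higher and neutrophils lower: some patients would be gained and others lost.
- Both figures as intended: nothing changes.

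The protocol supports no one of these over the others.

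**The case for a change.** The best argument for acting is that the written white-cell floor misdescribes the rule in force. A reader would suppose that patients with white cells a little above 3.0 can enter, when at 3.2 that takes 94% neutrophils. Unlike a condition that is merely listed twice, this is a separate numerical limit made inoperative. Checking two figures against the source costs almost nothing, and in a single-arm trial a wrong entry threshold shifts the population being described.

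The arithmetic stands in full, and asking the sponsor to confirm the figures is reasonable. The step from an odd line to a fault in the plan does not stand. The only sign of an error is that the two values are equal, and equal values are compatible with a deliberate choice. Overlap is also not foreign to this protocol: exclusion criterion 6 rules out liver decompensation "including those with refractory ascites, ruptured esophageal or gastric variceal bleeding, and hepatic encephalopathy", and criterion 8 names "hepatic encephalopathy, refractory ascites or hepatorenal syndrome" again, without harm. A site that applies item 5 literally reaches one answer for each patient, so the redundancy creates no room for inconsistent enrolment.

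**Conclusion.** The white-cell floor is redundant; that is certain, provided both counts come from the same sample and the figures were read correctly from the PDF. It removes zero patients beyond those the neutrophil floor removes. Eligibility as written is unambiguous, the two limits are compatible, and neither is shown to be wrong. No sample size, power or error rate depends on them.

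There is therefore no definite change to ask for, and no demonstrated gain in bias, precision or safety. Any real consequence would require an error in an operative text that is not at hand, and its size cannot be estimated because the protocol gives no distribution of counts. The point is an editorial query at most: the sponsor may confirm both figures against the operative protocol. Only if a correction would exclude patients whom the current text admits, including the mixed case above, would the entry counts of enrolled patients need a look. No threshold is suggested here.

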## **2. Exclusion Criteria:**

Any of the following circumstances shall be excluded and shall not be selected:

- 1) Pregnant or lactating women, men or women who do not wish to use effective contraception;
- 2) Patients who have received previous treatment with lysoviruses (e.g., T-VEC), interventional therapy, or TACE;
- 3) Those who are being treated with antiviral drugs;
- 4) having received any other experimental drug, antimicrobial drug, or participated in another interventional clinical trial within 4 weeks prior to enrollment
- 5) Those with a known allergy to the study drug or its active ingredient, or a history of allergy to similar biological agents
- 6) Evidence of Child-Pugh C hepatic function or hepatocellular dysregulation, including those with refractory ascites, ruptured esophageal or gastric variceal bleeding, and hepatic encephalopathy

- 7) presence of a history of immunodeficiency or autoimmune disease or long-term systemic steroid therapy or any form of immunosuppressive therapy within 7 days prior to enrollment
- 8) With any unstable systemic disease, including but not limited to: severe infection, hypertensive patients, uncontrolled diabetes mellitus, unstable angina pectoris, cerebrovascular accident or transient cerebral ischemia, abnormal mental status or active cerebral hemorrhage, myocardial infarction, congestive heart failure, severe arrhythmias requiring drug therapy, renal or metabolic disease, severe hepatic dysfunction (including severe jaundice, hepatic encephalopathy, refractory ascites or hepatorenal syndrome), multiple organ failure with renal dysfunction;
- 9) Previous or concurrent other malignancies;
- 10) Combined medical contraindications that preclude any contrast-enhanced imaging (CT or MRI);
- 11) Other conditions that, in the judgment of the investigator, make the patient unsuitable for participation in this study.

